6.4 Data Management & Statistical Considerations

6.4.1 Data Collection & Management

Staff will record all Aim 2 study de-identified data, obtained from IPT registry and “blue card” data (re: INH refills), and TB disease evaluation data (e.g. sputum microscopy results or x-ray results) using either paper lab logs, or password-protected study computers. Data from these logs or devices will be entered and transferred via a secure electronic transfer to our data center facility in Kampala and stored on a secure server.

6.5.2 Analysis

6.5.2.1 IPT completion:

Primary outcome: We will examine INH completion, defined as an indicator of dispensation of 180 pills of INH within 9 months of INH initiation, as the primary outcome of Aim 2 among sampled patient charts in intervention and control groups (see Section 6.5.3. below). The effect of SPIRIT on INH completion will be

[figure not shown]
estimated with TMLE, analogously to the primary endpoint of IPT uptake (see Section 5.7 above). We will account for clustering by randomization group and by DHO within randomization group. In all analyses, we will adjust for the sampling probability to make inferences about the target population of IPT-prescribed, HIV-infected persons in Uganda.

Figure 3 shows the effect size that we are powered to detect when IPT completion (as measured by hair levels) is 30-50% in the control arm. These calculations assume 30-40 patients sampled per DHO group, 12 DHO groups per arm, and a matched pair coefficient of variation $k_m=0.2$. Assuming IPT completion is 44% under the standard of care, we anticipate at least 80% power to detect a 40% increase in IPT completion due to the SPIRIT intervention (Figure 3).⁴⁴

Additional secondary analyses: We will examine the effect of SPIRIT on ART adherence and viral suppression in the sub-sample of patients for Aim 2.

Qualitative analysis: Data collection and analyses will be similar to those described for Aim 1.

Figure 3 (right): Effect size (in percent increase in IPT completion) detected with at least 80% varying the completion under the standard of care (SoC) and number of patients sampled per DHO group. We assume 12 DHO groups per arm and a matched pair coefficient of variation $km=0.2$.

[figure not shown]
6.5.2.2 TB incidence:

Primary outcome: We will examine the impact of the SPIRIT intervention on the incidence rate of TB among all HIV-positive adults at a health facility overseen by DHOs participating in the SPIRIT trial. The analysis of TB incidence in the population will mirror the primary analysis of Aim 1. Assuming an incidence rate 200 cases per 100,000 person-years in the standard of care,⁴⁵ and 10% completion of IPT (which conservatively reduces TB incidence by 40%,^{1,2} the incidence density method suggests a two-year cumulative incidence of approximately 0.38% in the control arm. Figure 4 shows the effect size that we are powered to detect when the control cumulative incidence is 0.35-0.40%.⁴⁴ Since the outcome is rare, these calculations are more sensitive to the number of patients per DHO group. However, we are relying on existing data collection systems (“blue card” forms and MoH TB clinic registries). Therefore, we anticipate capturing TB case reports on at least 3000 patients per DHO group. Assuming a control incidence of 0.38%, at least 2800 eligible patients in each DHO group, 12 DHO groups per arm, and a matched pair coefficient of variation $k_m=0.2$, we will be powered to detect 40% reduction in TB incidence in the overall population.

The analysis of TB incidence in the sub-sample of Aim 2 will mirror the analysis of IPT completion (Section 6.5.2.1). We will adjust for clustering and the sampling probability to make inferences about the target population of IPT-prescribed, HIV-infected persons in Uganda.

Figure 4: Effect size (in percent decrease in TB incidence) detected with at least 80% varying the incidence under the standard of care (SoC) and number of HIV-positive adults per DHO group. We assume 12 DHO groups per arm and a matched pair coefficient of variation $km=0.2$.

**Effect Size Detected with 80% Power
Varying the Number of HIV+ Adults
and TB incidence in the Standard of Care (km: 0.2)**

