6.2 IPT Completion

There is no gold standard for IPT completion in the field and prior studies have utilized patient self-report, pill counts, INH refill visits, and or blood/urine measures of INH metabolism.

INH refill visits will be measured from “blue card” clinic data or MoH IPT registries in the Aim 2 sub-sample (see Section 5.6.1. above). INH refill visit measurements will include both the number of refill visits (i.e. 5, if prescribed monthly), and the number of pills dispensed. INH completion by INH refill visit measurement will be defined as dispensation of 180 pills of INH within 9 months of INH initiation.

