We will focus on effect measures on the absolute scale and for the N districts with both baseline and follow-up data. Primary analyses will focus on the change from baseline to year-1. Secondary analyses will focus on change from baseline to year-2 and from year-1 to year-2. We will report point estimates and two-sided 95% confidence intervals for the arm-specific annual responses, the arm-specific estimates of change, and the effect estimates. Primary analyses will weigh the N districts equally and include all districts, including those created during follow-up. We will use the same approach to statistical inference as the primary endpoint.

Additional analyses: We will repeat the above analyses stratifying on whether the respondent is a DHO or a DTLSS.

5 Secondary outcome: IPT completion among persons starting IPT

A key intermediate between IPT uptake and TB prevention is IPT completion. Therefore, we will also assess the SEARCH-IPT intervention on “IPT completion”, defined as dispensation of a full course of IPT within 9 months of initiation. As detailed in the corresponding SOP, this endpoint will be measured among $N = 800$ (400 persons/arm) who are aged 15+ years, HIV-infected, and started IPT at one of 16 facilities in Southwestern region. Within each clinic, these participants will be sampled such that half initiated IPT before Q3-2019 and half initiated in Q3-2019 (during the “100-day IPT push”).

Data source: For each sampled participant, de-identified data on IPT completion (via INH pills dispensed over 9 months) will be obtained from the IPT register and blue cards. Additionally, data on the following variables will be recorded: gender, date of birth, marital status, ARV regimen, ARV switches while on IPT (date and new regimen), most recent HIV RNA viral load, if on Septrin or Dapsone while taking INH, and diagnosis of active TB.

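### The power stated for IPT completion takes its control rate from hair levels, which the trial does not measure; no control rate is given for the pills-dispensed endpoint that is analysed

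*Protocol*

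**What the plan says.** Protocol 6.2 (IPT Completion) sets the measure: "INH completion by INH refill visit measurement will be defined as dispensation of 180 pills of INH within 9 months of INH initiation". Protocol 6.5.2.1 repeats it for the Aim 2 primary outcome, "defined as an indicator of dispensation of 180 pills of INH within 9 months of INH initiation". SAP section 5 agrees, "defined as dispensation of a full course of IPT within 9 months of initiation", and names the source: "de-identified data on IPT completion (via INH pills dispensed over 9 months) will be obtained from the IPT register and blue cards".

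The power text in Protocol 6.5.2.1 introduces Figure 3 as the detectable effect when "IPT completion (as measured by hair levels) is 30-50% in the control arm". It assumes 30-40 patients per group, 12 groups per arm and a matched-pair coefficient of variation k_m of 0.2. For a control-arm value of 44% it then claims: "we anticipate at least 80% power to detect a 40% increase in IPT completion due to the SPIRIT intervention".

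Hair levels are mentioned nowhere else in either document. SAP Appendix 6.3 gives power for IPT uptake only, so nothing supersedes the protocol's statement for completion.

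**The concern.** A power statement is useful only if its control rate belongs to the endpoint that will be compared. Here the 30-50% range is attached to a drug-exposure measure, and the endpoint is a dispensing record. The two can differ in either direction. Pills can be collected and not taken, which would put dispensing above exposure. A course can also be missed in the register, interrupted by a stock-out or finished after nine months, which would put it below.

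This matters because the sized effect is relative. A 40% increase from 44% leaves ample room below 100%. From a high control rate it leaves little or none. Without a control rate for dispensing, the reader cannot judge which situation applies, or how to read a completion result that shows no difference.

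**Working it through.** **Inputs.** From Protocol 6.5.2.1: control completion p0 = 44%; increase 40%; c = 12 groups per arm; m = 30-40 patients per group; k_m = 0.2. From Protocol 5.7: two-sided 5% test. For the design run: 7 groups per arm (SAP section 1), 400 patients per arm (Protocol 6.5.3, SAP section 5), one-sided 5% test for completion (SAP section 5).

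**Formula.** The standard matched-pair formula for proportions:

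c = 2 + (z_α + z_β)² × [p0(1−p0)/m + p1(1−p1)/m + k_m²(p0² + p1²)] / (p1 − p0)²

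with (1.96 + 0.84)² ≈ 7.85.

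**1. The plan's figure.** Read as relative, p1 = 0.44 × 1.40 = 0.616 and (p1 − p0)² = 0.176² = 0.0310.
- m = 30: bracket = 0.0082 + 0.0079 + 0.0229 = 0.0390; c = 2 + 7.85 × 0.0390/0.0310 = 11.9; power with 12 groups is 80.4%.
- m = 40: bracket = 0.0062 + 0.0059 + 0.0229 = 0.0350; c = 10.9; power is 84.5%.

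This matches the stated figure. Reading the 40% as absolute (44% to 84%) gives power of about 100%, so the sized effect is relative, as the Figure 3 caption also indicates.

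**2. What this shows.** The formula uses a proportion and a coefficient of variation; it does not know how completion was measured. If control dispensing is 44%, the stated power holds under the plan's other inputs. The defect lies in where the input comes from.

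**3. Ceiling.** A 40% relative increase reaches 100% when p0 = 1/1.40 = 71.4%. At an assumed 75% control the largest possible increase is 33% (1/0.75 = 1.33); at 80% it is 25%.

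**4. Detectable completion at other control rates.** The documents give no control dispensing rate, so the rates below other than 44% are assumptions. Table: smallest intervention-arm completion detectable with 80% power, 12 groups per arm, m = 40, two-sided 5%. The second column holds k_m at 0.2. The third holds the intracluster correlation implied at 44%, ρ = k_m² p0/(1−p0) = 0.04 × 0.44/0.56 = 0.031, and replaces the k_m term by ρ[p0(1−p0) + p1(1−p1)].

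| Control | Constant k_m = 0.2 | Constant ρ = 0.031 |
|---|---|---|
| 44% | 60% | 59% |
| 50% | 68% | 65% |
| 60% | 80% | 74% |
| 70% | 92% | 83% |
| 75% | 98% | 87% |
| 80% | none | 90% |
| 85% | none | 94% |

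The entries "none" arise because a constant k_m = 0.2 gives the intervention arm a between-group SD of 0.20 even when every group is at 100%, which cannot happen. With that arm's between-group variance set to zero at 100%, the required c at 80% control falls from 15.7 to 7.8, and the control rate at which 100% completion is no longer detectable moves from about 77% to about 84%. With constant ρ there is no such limit up to 85%.

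**5. Design actually run.** With 7 groups per arm and 400/7 ≈ 57 patients per group, the same formula for 44% against 61.6% gives about 60% power two-sided and 72% one-sided. This is still only a group-level approximation. SAP section 5 samples from 16 Southwestern facilities and uses an individual-level TMLE, and Protocol 9.2.1 puts only 2 intervention and 2 control groups in that region.

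**The case against.** The hair-level phrase may be a leftover. The sentence with 44% and the Figure 3 caption do not repeat it, the figure cannot be seen, and the same power follows if control dispensing is 30-50%. Completion is a secondary outcome of the trial, and the sample is fixed at 400 per arm. All of this is fair, and it makes this a point about the source of an input rather than an error of arithmetic. It does not remove the point: deleting the phrase alone would leave 44% and 30-50% with no stated basis for dispensing.

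Two stronger readings are tempting.
- **That control dispensing must be higher than 30-50%, so the sized effect is out of reach.** The documents do not support this. They give no hair-level threshold, so an exposure cut-off might be met with fewer than 180 pills. Protocol 5.6 concedes that routine records may be incomplete, and SAP section 1 describes a severe drug shortage up to the end of 2018; either could lower recorded dispensing. Nothing shows a control rate above 50%, let alone 71%.
- **That the comparison is uninformative above roughly 77% control.** That limit comes from holding k_m = 0.2 at 100% completion, as step 4 of the working shows.

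Nor would a ceiling be hidden in the results. SAP section 5 commits to arm-specific means, absolute and relative effects with two-sided 95% confidence intervals, and total completions by arm.

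**Conclusion.** The point holds as a mismatch of inputs. The trial's only power statement for IPT completion is tied to a measure it does not collect, and no control rate is given for the endpoint it analyses. The stated power of at least 80% reproduces and would stand, for 12 groups per arm, if control dispensing were 44%; whether it is cannot be read from the documents.

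The size of the consequence depends on two things the plan does not state: the control dispensing rate and how between-group variance behaves as completion rises. At an assumed 70% control, detectable completion is about 92% with constant k_m and about 83% with constant intracluster correlation (a difference of 22 or 13 points, against about 16 points from 44% under the plan's k_m). The 71.4% ceiling is exact but conditional. The group count is a separate defect in the same calculation, and it has to be corrected together with this one if the restated figure is to describe the analysis.

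**What to change.** In Protocol 6.5.2.1, and in Figure 3 if it is labelled that way:
- Remove the reference to hair levels.
- Justify the 44% and the 30-50% range for 180 pills dispensed within nine months, or replace them. Label them as planning assumptions, and do not draw them from the unblinded completion results.
- Restate the detectable effect as an absolute difference over a wider assumed control range, for example 30-85%.
- State the between-group variance assumption, preferably showing both constant k_m and constant intracluster correlation, since k_m = 0.2 is not credible near 100%.
- Note that a 40% relative increase cannot occur if control dispensing exceeds 71.4%.
- Do the recalculation for the design run: 7 groups per arm, 400 patients per arm, the SAP's 16-facility Southwestern sampling frame and its one-sided test. Say which unit is treated as independent.

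The cost is a text edit and one recalculated figure. The stated power may become less favourable. Sampling, data collection and trial conduct do not change.

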1.1 Study Synopsis

We will evaluate the effect of the SPIRIT intervention on provider prescription and patient use of a 6-month course of IPT among all adults in HIV care in Uganda. SPIRIT is a multicomponent intervention based on the PRECEDE model of behavioral change targeted primarily at the level of the DHO. The SPIRIT intervention deploys predisposing (teaching collaborative); enabling (SMS); and reinforcing (reporting collaborative) components. The study design is a cluster randomized trial where the unit of randomization is a group of 4-6 DHOs: seven groups randomized to the intervention and seven to the current country standard of care. The primary endpoint of the study is the rate at which eligible HIV-positive adults (defined by the Ugandan Ministry of Health) receive a prescription for INH in health facilities overseen by DHOs participating in the SPIRIT trial. Secondary endpoints include: a) IPT completion measured through analyzing successful INH refill patient-visits; b) DHO and health worker attitudes towards IPT; c) TB incidence; d) DHO leadership and management skills and e) costing and cost-effectiveness. The overall goal of the proposal is to test the effectiveness of a scalable approach to increasing IPT uptake through a behavioral change model targeting DHOs (middle managers) within the Uganda health infrastructure. In a second phase of the trial (Phase 2: Years 4-5), we will: a) evaluate the impact of enhanced business management training, focused on SPIRIT intervention DHOs in

the Southwestern Uganda region, on IPT initiation in the region during Phase 2; and b) implement a training of trainers (ToT) curriculum among DHOs enrolled in the SPIRIT trial from the southwestern region of Uganda to determine if DHO-provided business management training of their District Health Team (DHT) members can improve the management skills of the DHT members. **Figure 1** provides a schematic overview of the SPIRIT study:

Figure 1. SPIRIT study schema. For illustration we show 10 DHO groups per arm with 5 DHOs per group. The trial will enroll 14 DHO Groups: 7 intervention and 7 control. In Years 4 and 5 (Phase 2), the trial will be limited to the 14 districts in the Southwestern region of Uganda.

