5.2 Randomization

The SPIRIT trial investigators will form up to 14 groups of 4-7 DHOs (Figure 1). When possible, groups will be formed based on geographic, socio-demographic, and health systems characteristics. The groups will be pair-matched on geographical, socio-demographic and health systems characteristics to improve statistical efficiency. For both the creation of the groups and construction of matched pairs, geographic proximity will be optimized to facilitate DHO mini-collaboratives in the SPIRIT intervention and minimize contamination between arms. Randomization will be performed using a random number generator in standard statistical software, and overseen by the study statistician. One group in each of the 7 matched pairs will be randomized to the intervention, and one to the control condition.

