5.7.2 Sample Size & Accrual

Sample size considerations for the primary outcome of IPT uptake: In the control condition (standard of care), we anticipate 10% of eligible individuals will receive IPT. We anticipate that 50% of eligible individuals will receive IPT in the intervention condition. Assuming 12 DHO groups per arm and an extremely conservative matched pair coefficient of variation k_m of 0.4, this study will be powered at >95% (Figure 2).⁴⁴ If we more than double the anticipated rate of IPT use in the control condition to 25% (vs. 50% in the treatment condition), the power remains at >90%. Of note, unlike a traditional sample size calculation where the investigators must “enroll” to reach a desired sample size, we use routine health systems data and therefore calculate anticipated power from a fixed sample size based on the number of DHO groups. As shown in Figure 2, these power calculations are not sensitive to the number of patients enrolled in each DHO group. We expect 1,000-25,000 patients in each DHO group.

Figure 2 (right): Power calculations for the primary outcome of IPT uptake, assuming 12 DHO groups per arm and varying the outcome among the standard of care (SoC) and the number of patients

6. IPT Adherence & TB Incidence in the SPIRIT Trial

Rationale: The population health impact of our DHO intervention aimed at reducing TB depends not only on IPT prescribing, but also on adherence and completion of IPT by patients. Thus, to understand the implementation pathway, it is important to measure an adherence outcome, which we propose to assess through the analyses of INH refill visits, as metrics of long-term pill consumption. Because ART use can both affect risk for TB in HIV+ persons, and be indirectly affected by our DHO intervention, we will also measure ART refills in our sampled subset of Aim 2. As another secondary outcome, TB incidence contributes to quantifying the magnitude of the public health effect of SPIRIT.

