Sustainable East Africa Research in Community Health
(SEARCH) Collaboration

**Statistical Analysis Plan for Health Outcomes
in Phase 1 of the SEARCH-IPT Study**

[name], PhD¹
[name], MS¹
[name], MD²
[name], MD²

November 10, 2021
Version 2.1

¹University of Massachusetts, Amherst; ²University of California, San Francisco

Contents

1	Brief study overview	2
2	Primary outcome: IPT uptake	4
3	Secondary outcome: HIV-associated TB incidence	7
4	Secondary outcome: Knowledge, attitudes, and practices regarding IPT	8
5	Secondary outcome: IPT completion among persons starting IPT	9
6	Appendix	11
6.1	History of changes:	11
6.2	Select survey questions:	11
6.3	Power calculations:	12

1 Brief study overview

The SEARCH-IPT Study is a cluster randomized trial designed to evaluate whether a multicomponent intervention increases uptake of isoniazid (INH) preventive therapy (IPT) and reduces the incidence of tuberculosis (TB) in Uganda (Clinicaltrials.gov: NCT03315962). Details of the multiphase trial design and procedures can be found in the Study Protocol. Here, we provide the statistical analysis plan for health outcomes in Phase 1 of the study. Analysis plans for qualitative outcomes, cost-effectiveness outcomes, and business outcomes are available elsewhere. A history of changes to this analysis plan is given in the Appendix.

Study design: Phase 1 of the SEARCH-IPT Study aims to increase provider prescription and patient use of IPT among adults in HIV care in Uganda. Within the Eastern, East-Central, and Southwestern regions of Uganda, districts were first grouped into 14 clusters of 4-7 districts. To improve statistical power [1, 2], these groups were pair-matched on characteristics expected to be predictive of IPT uptake: region, number of adults in active HIV care, urbanicity, and presence of a SEARCH universal HIV “test and treat” trial site. Within each pair, the groups were then randomized to intervention or the standard-of-care. There are 7 groups in each arm. Formal power calculations are given in the Appendix.

Study arms: In districts randomized to the intervention, the groups are the mini-collaboratives

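### Protocol power is stated for 12 DHO groups per arm but 7 are randomised, and no 7-group figure exists for TB incidence or IPT completion

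*Protocol*

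**What the plan says.** **Power statements.** Protocol 5.7.2 (uptake) begins "Assuming 12 DHO groups per arm and an extremely conservative matched pair coefficient of variation" and takes km = 0.4. It gives more than 95% power for 10% vs 50% and more than 90% for 25% vs 50%. Protocol 6.5.2.1 (completion) claims at least 80% power for a 40% relative increase from 44%, with 12 groups per arm, 30-40 patients per group and km = 0.2. Protocol 6.5.2.2 (TB) assumes a control two-year incidence of 0.38%, "at least 2800 eligible patients in each DHO group, 12 DHO groups per arm" and km = 0.2, and concludes that "we will be powered to detect 40% reduction in TB incidence in the overall population". The captions of Figures 2-4 also give 12 groups per arm.

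**Design.** Protocol 1.1: "The trial will enroll 14 DHO Groups: 7 intervention and 7 control". Protocol 5.2: "One group in each of the 7 matched pairs will be randomized to the intervention, and one to the control condition". SAP section 1: "There are 7 groups in each arm".

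**What the SAP updates.** SAP 6.3 gives power at 7 groups per arm, one-sided, for uptake. It has no line for TB or completion.

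**Completion.** The outcome is 180 INH pills dispensed within 9 months (Protocol 6.2 and 6.5.2.1), but the power text in 6.5.2.1 refers to completion judged by hair levels. Protocol 6.5.3 samples at least thirty patients in each DHO group, 400 per arm. SAP section 5 takes its 800 patients from 16 facilities in the Southwest. Protocol 9.2.1 places 2 intervention and 2 control groups in that region.

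**The concern.** The number of randomised groups largely fixes the power of a cluster trial. Going from 12 to 7 per arm cuts the usable units in the matched formula from 10 to 5, so a stated 80% cannot carry over if the other inputs stay the same. For uptake, the SAP gives a replacement figure. For TB and completion there is none, so a reader who asks what the trial could detect on those outcomes finds only numbers for a design that is not being run. TB incidence is part of the trial's stated overall objective and has its own one-sided 5% test in SAP section 3, so its power statement will be used when the result is interpreted.

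**Working it through.** **Formula.** The protocol cites a standard cluster-trial text. The matched-pair version for proportions is

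c = 2 + (z_α + z_β)² × [ (p0(1−p0) + p1(1−p1))/n + km²(p0² + p1²) ] / (p0 − p1)²

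with c groups per arm and n patients per group. Solved for power: z_β = √[(c − 2)(p0 − p1)² / V] − z_α, where V is the square bracket. z_α is 1.960 two-sided (Protocol 5.7) or 1.645 one-sided (SAP).

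**Step 1: reproduce the protocol (c = 12, two-sided).**
- TB: p0 = 0.0038, p1 = 0.00228, n = 2,800, km = 0.2. V = 2.164×10⁻⁶ + 0.786×10⁻⁶ = 2.950×10⁻⁶ and (p0 − p1)² = 2.310×10⁻⁶. √(10 × 2.310/2.950) = 2.799, so z_β = 0.839 and power is 79.9%.
- Completion: 0.44 vs 0.616, n = 30, km = 0.2. V = 0.01610 + 0.02292 = 0.03902 and (p0 − p1)² = 0.03098. √(10 × 0.03098/0.03902) = 2.818, so power is 80.4%.
- Uptake: 0.25 vs 0.50, n = 1,000, km = 0.4. V = 0.0004 + 0.0500 = 0.0504 and (p0 − p1)² = 0.0625. Power is 94.1%.

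The protocol's arithmetic is sound for 12 groups per arm.

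**Step 2: change only c to 7.** The factor 10 becomes 5.

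| Outcome | Stated | 7 per arm, two-sided (one-sided) |
|---|---|---|
| TB, 40% reduction, n = 2,800 | 80% | 51% (63%) |
| Completion, n = 30 | at least 80% | 51% (64%) |
| Completion, n ≈ 57 (400/7) | no figure | 60% (72%) |
| Uptake 25% vs 50% | >90% | 70% (80%) |
| Uptake 10% vs 50% | >95% | 99% (>99%) |

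For TB, √(5 × 2.310/2.950) = 1.979, so z_β = 0.019 two-sided and 0.334 one-sided. Unmatched and t-based variants were also tried. With 7 groups and the stated inputs, none reached 80% for TB or completion.

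**Step 3: TB with larger groups (c = 7, 40% reduction).** At km = 0.2, 80% power needs about 8,800 (5,600) patients per group. The TB group size is not given for the SAP's district-wide data. As an assumption, SAP 6.3's 21,500 person-years over two years is 10,750 people per group. Power is then 97% (99%) at km = 0.1, 83% (90%) at km = 0.2 and 61% (72%) at km = 0.3.

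**Step 4: SAP 6.3.** The unmatched rate formula, c = 1 + (z_α + z_β)²[(λ0 + λ1)/y + k²(λ0² + λ1²)]/(λ0 − λ1)², with c = 7, one-sided, k = 0.25 and y = 21,500, gives 81% for 22 vs 32 and 80% for 30 vs 43.5 per 100 person-years. The SAP's uptake figures therefore stand.

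**Step 5: completion under the SAP's sampling.** With 2 groups per arm, c − 2 = 0 and the matched formula gives no usable power. Treating clinics as units (assumed 8 per arm, 50 patients each, coefficient of variation 0.2) gives 67-73% two-sided and 77-83% one-sided across the matched and unmatched versions. The answer depends on the unit chosen, and the documents give no power on either basis.

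**The case against.** The strongest reply is that this is text left over from a larger design, with correct arithmetic, and that the SAP has moved on. For uptake that largely stands: SAP 6.3 gives valid 7-group figures, and the protocol's main scenario (10% vs 50%) keeps its power. It fails for TB and completion, because no later figure replaces the 12-group ones.

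A second reply is that 2,800 per group is a floor and the SAP's TB data are district-wide. This has force. At 10,750 per group and the stated km, power for a 40% reduction is 83% (90%). The SAP's unmatched one-sided rate formula, with control incidence 200 × (1 − 0.1 × 0.4) = 192 per 100,000 person-years, gives 94% at k = 0.2 and 87% at k = 0.25. A reader might infer that the TB analysis is underpowered for a 40% reduction; the documents do not support that. They support only that the claim is not met at the inputs given for it.

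A third reply is that the SAP's primary analysis breaks the pairs, counts 7 + 40 units and adjusts for covariates, so its power may differ. True, but SAP 6.3 itself uses the randomised groups as its conservative unit.

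It is also tempting to read 51% or 60% as the completion power of the trial. It is not: those figures assume sampling across all 14 groups, which SAP section 5 does not do, and the SAP's main completion analysis is at individual level.

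**Conclusion.** The concern holds for the stated figures. The randomised design of 7 groups per arm does not deliver the protocol's power at the protocol's own inputs: 51% (63%) instead of 80% for TB, 51-60% (64-72%) instead of at least 80% for completion, and 70% (80%) instead of more than 90% for uptake at 25% vs 50%. These rest on the matched formula with randomised groups as units and the stated km values. The primary outcome is not in doubt.

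Whether TB power is adequate is open: it turns on group size and km, which is why it needs restating. Nor is the 40% reduction an expected effect; the protocol gives it as detectable. Its own inputs, "10% completion of IPT (which conservatively reduces TB incidence by 40"% and "We anticipate that 50% of eligible individuals will receive IPT in the intervention condition", imply a direct reduction of 1 − (1 − 0.5 × 0.4)/(1 − 0.1 × 0.4) = 1 − 0.80/0.96 = 16.7% if every starter completes, ignoring reduced transmission. A reader might try to derive a planned TB effect from the uptake difference in SAP 6.3, but that is a detectable difference, not a planned uptake.

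The completion figure has no valid counterpart at all, since its measure and its sampling both differ from the plan.

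**What to change.** 1. **Protocol 5.7.2:** replace the 12-group figures with 7-group figures, or refer to SAP 6.3.
2. **Protocol 6.5.2.2, or a TB line in SAP 6.3 marked as added after lock:** give TB power, or the smallest detectable reduction, for 7 groups per arm under the SAP's one-sided 5% test, at the group sizes expected from district-wide data and over a range of km (for example 0.1-0.3). Optionally set beside it the direct reduction of about 17%, with its assumptions.
3. **Protocol 6.5.2.1:** withdraw the 12-group, hair-level figure. Decide which sampling stands, Protocol 6.1 and 6.5.3 or SAP section 5, and align the documents. Then restate power for the 180-pill outcome, naming the unit of independence and the assumed between-cluster variation.

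The cost is wording, one decision on completion sampling, and some less favourable power figures. No extra patients or data are needed, and the uptake and TB analyses do not change.
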